8.5.2.2 Follow-up

The investigator or his/her designee should follow all adverse events occurring during the study, with unrelated adverse events followed until the end of the final visit, and related AEs followed until the adverse event returns to normal or baseline or stabilizes, or the abnormality is deemed by the investigator to be not clinically significant, or is reasonably explained, or the participant is lost to follow-up or dies. All AEs in the study must be treated and documented. Any waivers must be approved by the sponsor's safety contact.

For related adverse events, the investigator should follow up until any of the following is achieved:

- Events resolved or stabilized;
- The event returns the baseline level, if a baseline value is available;
- The investigators conclude that the abnormalities are not clinically significant;
- Events can be attributed to drugs other than the investigational drug or to factors unrelated to the study behavior;
- When more information is unlikely to be available again (patient or healthcare professional refuses to provide more information, or there is evidence that the patient is still missing visits after best efforts have been made).

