8.5.3 Adverse Event Recording

The investigator should give detailed instructions to the participant and ask the participant to respond truthfully to changes in condition after administration of the medication. Physicians should avoid inducing questions. While observing the efficacy of the treatment, close attention should be paid to observing the adverse events, analyzing the causes, making judgments, and conducting follow-up observations and records.

All adverse events occurring between the signing of the informed consent and the end of the last visit must be documented in the appropriate section of the CRF (including the name of the adverse event, start/end time, severity, duration, whether it is a serious adverse event, severity criteria (if applicable), measures taken on the test medication as a result of the adverse event, causal relationship between the adverse event and the investigational drug, outcome, etc.) and recorded in detail in the study medical record, whether or not they are study-related, with the exception of participants who have withdrawn Informed consent and/or participants who are unable to be followed up are excluded.

The investigator should assess the possible association between the adverse event and the investigational drug and coadministration of the drug, as categorized in [8.5.4.2 Assessment of Causality](#). The severity of the adverse event will be graded according to CTCAE version 5.0. For each symptom, when there is a change in severity level, the change in severity level needs to be documented in detail, and any increase or decrease in severity needs to be documented.

Any recurrence, worsening, or exacerbation of an AE after remission or return to baseline condition will be documented as a new AE. All AEs should be documented in standard medical terminology whenever possible. The documented AE should not be an operation (e.g., surgical procedure) or a clinical or laboratory test, but rather reflect a known cause leading to the operation or clinical/laboratory test. If applicable, the AE should be evaluated and documented according to the diagnosis, not the participant's signs and symptoms. However, it may be recorded as the participant's signs and symptoms if a definitive diagnosis is not possible.

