All SAEs, whether treatment-related or not, that occur between the time of signing the informed consent and the end of the last visit are to be recorded. SAEs that occur at the end of the trial or after the end of follow-up until the conclusion of the review need to be reported to the sponsor if the investigator considers them to be related to the investigational drug.

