8.5.4.2 Causality Assessment

- Investigators should use their medical knowledge to consider the circumstances surrounding the event, and evaluate any potential alternative causes prior to making a final causality assessment, i.e., whether there is a reasonable possibility that the study drug caused the adverse event. The Investigator should provide the rationale or evidence to support the causality assessment as needed. The causality will be assessed according to the five-level classification criteria as follows:
- Positively related: The occurrence of AE is determined pharmacologically and is reasonably temporally related to the investigational drug. AE disappears or alleviates after discontinuation or reduction, and reappears after re administration. AE is not related to concomitant medication or non-pharmacological factors (food, participant's own illness, environment, etc.);
- Probably related: The occurrence of AE is reasonably temporally related to the investigational drug. AE disappears or alleviates after discontinuation or reduction. AE is not related to concomitant medication or non-pharmacological factors;
- Possibly related: The occurrence of AE is reasonably temporally related to the investigational drug. Remission of the AE after discontinuation or reduction is unknown or insignificant, and other factors (e.g., participant's own illness, concomitant medication, or non-pharmacological factors) may also contribute to the event;

- Possibly unrelated: The time relationship between the occurrence of AE and investigational drug administration is unclear. AE does not resolve after discontinuation or remission is unknown, and concomitant medication or non-pharmacological factors can explain the AE;
- Definitely unrelated: The occurrence of AE is not reasonably temporally related to the investigational drug and/or evidence exists that the AE is definitely related to concomitant medication or non-pharmacological factors.

Because this study is a single administration and does not involve observation of adverse events through dose reduction/discontinuation/re-use, the investigator should make a comprehensive judgment of relevance based on the metabolic and pharmacodynamic characteristics of the investigational drug and the participant's clinical presentation, as well as the possible presence of non-pharmacological factors. When there is a change in consistency among test individuals, it is more likely to be related to the investigational drug.

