In order to minimize risk to the medication-using population and to comply with regulatory requirements, sponsors will address the relevance of the incident in the following manner:

- "Possibly unrelated", "Definitely unrelated", i.e. "unrelated", are categorized as unrelated adverse events;
- "Positively Related", "Probably Related", or "Possibly Related" should be considered "Related" and categorized as related adverse events.

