8.5.5 Serious Adverse Event Reporting

8.5.5.1 Serious Adverse Event Reporting

When an investigator is informed of a serious adverse event in a participant during a clinical study, he or she should promptly manage and treat the event, whether or not the serious adverse event is related to the investigational drug. It should also be reported immediately (within 24 hours) to the sponsor or the sponsor's designated representative, and the investigator should complete, sign and date the full Drug Serious Adverse Event Report Form.

For reports involving fatal events, the investigator should provide other required information such as autopsy reports and final medical reports to the sponsor and ethics committee.

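### Section 8.5.2.2 ends required follow-up of unrelated adverse events at the final visit with no exception for serious ones, so a non-fatal unrelated SAE still open then has no general duty of outcome follow-up

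*Protocol*

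**What the plan says.** Section 8.5.2.2 divides follow-up by relatedness. Related events are followed until they resolve, stabilise, return to baseline or reach another listed end point. The rule for the rest is "with unrelated adverse events followed until the end of the final visit". No separate rule is given for serious events.

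Section 8.5.4.2 grades causality in five classes and then reduces them to two. The lower two classes, *Possibly unrelated* and *Definitely unrelated*, "are categorized as unrelated adverse events". The definition of the first begins "Possibly unrelated: The time relationship between the occurrence of AE and investigational drug administration is unclear" and continues "AE does not resolve after discontinuation or remission is unknown, and concomitant medication or non-pharmacological factors can explain the AE".

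The final visit is D29 with a window of ±2 days. Early withdrawal shares that column of Table 1, and 7.1 asks for an early-withdrawal visit only where possible.

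On serious events, 8.5.5.1 tells the investigator to "promptly manage and treat the event, whether or not the serious adverse event is related to the investigational drug", and to report within 24 hours. Further material is requested only in one case: "For reports involving fatal events, the investigator should provide other required information such as autopsy reports and final medical reports". Under 8.5.3, SAEs that occur after follow-up has ended go to the sponsor "if the investigator considers them to be related to the investigational drug".

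**The concern.** Relatedness is a reasonable basis for ending follow-up of minor events. It is a weaker basis for serious ones, for three reasons.

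- The causality call is uncertain by construction. *Possibly unrelated* is partly defined by unclear timing, and 8.5.4.2 acknowledges that a single-dose study offers no dose reduction, discontinuation or re-use to inform the judgement. The later course of the event is some of the evidence that could change the class, and the rule stops collecting it.
- The sponsor has a stake too. Under 8.5.1.3 relatedness for SUSAR purposes may rest on the sponsor's evaluation as well as the investigator's, and an open case gives the sponsor less to evaluate.
- An adverse event is itself a ground for withdrawal under 7.1. A participant with an SAE may therefore be the one whose final visit comes early, or is not held.

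What is at stake is the completeness of a few safety entries. Section 9.3.4 plans to report duration and resolution and to list outcome. For this kind of event those items could remain at ongoing.

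**Working it through.** The plan states no figure to reproduce. The check is whether any provision obliges the site to follow a non-fatal unrelated SAE beyond the final visit, and then how long the required follow-up can be.

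**Step 1: the provisions side by side.**

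| Protocol section | What it requires | Outcome follow-up past the final visit for an open, non-fatal, unrelated SAE? |
|---|---|---|
| 8.5.2.2, unrelated AEs | Follow to the final visit | No; this is where it ends |
| 8.5.2.2, treat and document all AEs | Treatment and documentation | No; no duration is set |
| 8.5.2.2, waivers | Sponsor approval of waivers | No; extends nothing |
| 8.5.3, AE recording | End time, outcome and severity changes, related or not | No; ongoing at the last visit satisfies it |
| 8.5.3, SAE recording | All SAEs occurring up to the last visit; later ones only if considered related | No; concerns occurrence, not outcome |
| 8.5.5.1, SAE reporting | Manage, treat and report every SAE within 24 hours | No; final reports are asked for fatal events only |
| 8.4.3, ECG | Abnormal ECG followed to resolution, whatever the cause | Only for the ECG finding |
| 8.5.6, pregnancy | Pregnancies followed to outcome, including maternal complications | Only for pregnancy cases |

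No row supplies a general duty. The last two supply narrow ones, and fatal events are covered separately.

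**Step 2: length of required follow-up.** Let t be the study day of onset and v the study day of the final visit or early-withdrawal visit. Required follow-up is v − t days, counted the same way for completers and withdrawals.

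- Completers: v lies between 29 − 2 = 27 and 29 + 2 = 31.
- Longest case for an onset on or after D1: 31 − 1 = 30 days.
- Shortest case: onset on the day of the visit, 0 days.
- Early withdrawal, illustration: onset D2, withdrawal visit D20, 20 − 2 = 18 days.
- An SAE that begins after consent but before dosing is also recorded as an AE (8.5.2.1), and its interval can be longer than 30 days.

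**Step 3: end points for the contrast group.** Section 8.5.2.2 lists 5 end points for related events. One turns on causality (attribution to other drugs or to factors unrelated to the study). That leaves 5 − 1 = 4 that could serve for SAEs whatever their cause.

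**Step 4: how many participants.** The documents give no probability for such an event. The 2020 study at 300 U/kg in healthy subjects (4.3) recorded 0 SAEs in 10 subjects. Here about 22 are planned, and the event would have to be serious, non-fatal, judged unrelated and still open at the visit.

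**The case against.** The strongest reply is that 8.5.2.2 contains no error. It is an explicit rule with a defined end, and it matches the AE monitoring period in 8.5.2.1 and the SAE recording window in 8.5.3. Ongoing is a legitimate outcome, and 9.3.4 does not promise that every event will be resolved. *Possibly unrelated* also requires that other factors can explain the event. With a half-life of about 40 hours (2.2.1), D27 to D31 is 26 to 30 days after dosing, or 624/40 = 15.6 to 720/40 = 18 half-lives, so little drug should remain.

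Much of this stands. The rule is internally consistent, and the point is a design choice that could be better, not a contradiction. The half-life argument is weaker than it looks because the platelet response outlasts the drug. In the 2.0 µg/kg group described in 4.3, about twice this trial's dose, platelets were still 262 against a baseline of 209 ×10⁹/L on day 21. The argument about ongoing entries does apply to non-serious events as well. Serious ones differ in what later worsening would mean for the participant and for the sponsor's assessment.

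A reader might also infer more than the documents support:

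- **That unrelated SAEs escape recording or reporting.** They do not. Sections 8.5.3 and 8.5.5.1 capture occurrence, grade and causality whatever the relationship.
- **That no SAE of this class is ever followed past the final visit.** Sections 8.4.3 and 8.5.6 create exceptions, though narrow ones.
- **That participants who withdraw early get no follow-up.** Theirs also runs from onset to the withdrawal visit; it is shorter, not nil by rule.

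**Conclusion.** The point holds in a limited form. Required follow-up of an unrelated SAE ends at the final or early-withdrawal visit. For a non-fatal event still open then, outside the ECG and pregnancy rules, no general duty exists to obtain the outcome. Required follow-up is at most about 30 days for an onset on or after D1, and can be 0.

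This rests on the protocol text alone. It assumes that no other safety document, such as a safety management plan, adds the duty; 8.5.2.2 refers to none. It is not a matter for the SAP, because safety follow-up is site conduct that the protocol itself fixes.

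It would be wrong to conclude that the safety results are materially biased. Incidence, grade and causality up to the visit are complete, the PK primary endpoint is unaffected, and the number of participants concerned may well be 0. This is a cheap improvement at the lowest severity.

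**What to change.** Make two edits to 8.5.2.2, which need to go together because the added sentence alone would contradict the existing clause.

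1. Insert *non-serious* before *unrelated* in the clause that ends follow-up at the final visit.
2. Add: *All SAEs in dosed participants, whatever the causality, are followed until resolved or stabilised, returned to baseline, judged not clinically significant, or no further information is obtainable, including after early withdrawal unless consent to contact is withdrawn.*

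The sentence reuses the four listed end points that do not turn on causality. Limiting it to dosed participants keeps screen failures who never received drug outside the duty.

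The cost is an occasional outcome enquiry after the final visit. Information that arrives after database lock can be handled under the existing post-lock rule in A 4.3, which allows a confirmed database update or an explanation in the report with a written record. The site already carries a longer duty of this kind for pregnancies.

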8.5.3 Adverse Event Recording

The investigator should give detailed instructions to the participant and ask the participant to respond truthfully to changes in condition after administration of the medication. Physicians should avoid inducing questions. While observing the efficacy of the treatment, close attention should be paid to observing the adverse events, analyzing the causes, making judgments, and conducting follow-up observations and records.

All adverse events occurring between the signing of the informed consent and the end of the last visit must be documented in the appropriate section of the CRF (including the name of the adverse event, start/end time, severity, duration, whether it is a serious adverse event, severity criteria (if applicable), measures taken on the test medication as a result of the adverse event, causal relationship between the adverse event and the investigational drug, outcome, etc.) and recorded in detail in the study medical record, whether or not they are study-related, with the exception of participants who have withdrawn Informed consent and/or participants who are unable to be followed up are excluded.

The investigator should assess the possible association between the adverse event and the investigational drug and coadministration of the drug, as categorized in [8.5.4.2 Assessment of Causality](#). The severity of the adverse event will be graded according to CTCAE version 5.0. For each symptom, when there is a change in severity level, the change in severity level needs to be documented in detail, and any increase or decrease in severity needs to be documented.

Any recurrence, worsening, or exacerbation of an AE after remission or return to baseline condition will be documented as a new AE. All AEs should be documented in standard medical terminology whenever possible. The documented AE should not be an operation (e.g., surgical procedure) or a clinical or laboratory test, but rather reflect a known cause leading to the operation or clinical/laboratory test. If applicable, the AE should be evaluated and documented according to the diagnosis, not the participant's signs and symptoms. However, it may be recorded as the participant's signs and symptoms if a definitive diagnosis is not possible.

All SAEs, whether treatment-related or not, that occur between the time of signing the informed consent and the end of the last visit are to be recorded. SAEs that occur at the end of the trial or after the end of follow-up until the conclusion of the review need to be reported to the sponsor if the investigator considers them to be related to the investigational drug.

8.5.4 Assessment of Adverse Event

8.5.4.1 Severity Classification

Adverse drug events will be determined with reference to the Common Terminology Criteria for Adverse Events (CTCAE) (version 5.0) criteria for grading adverse events, and parameters not covered by CTCAE 5.0 may be interpreted, at the investigator's judgment, on the basis of the CTCAE Base Guidelines for Severity Grading or in a similar manner. The CTCAE 5.0 Base

Guidelines for Grading are as follows:

- Grade 1: Mild; asymptomatic or mild symptoms; clinical or diagnostic observations only; no treatment required.
- Grade 2: Moderate; minimal, local or non-invasive intervention required; limiting age-appropriate instrumental activities of daily living (e.g., cooking, shopping, using telephone and managing money, etc.).
- Grade 3: Severe or medically significant but not immediately life-threatening; hospitalization or prolonged hospitalization indicated; disabling; limiting self-care activities of daily life (e.g. bathing, dressing and undressing, feeding self, using toilet, and taking medications), but not bedridden.
- Grade 4: Life-threatening; urgent intervention required.
- Grade 5: Death related to AE.

Symptoms and signs should be described using clear, standardized, and recognized professional medical terminology, avoiding colloquial language that is vague and likely to lead to ambiguity.

8.5.4.2 Causality Assessment

- Investigators should use their medical knowledge to consider the circumstances surrounding the event, and evaluate any potential alternative causes prior to making a final causality assessment, i.e., whether there is a reasonable possibility that the study drug caused the adverse event. The Investigator should provide the rationale or evidence to support the causality assessment as needed. The causality will be assessed according to the five-level classification criteria as follows:
- Positively related: The occurrence of AE is determined pharmacologically and is reasonably temporally related to the investigational drug. AE disappears or alleviates after discontinuation or reduction, and reappears after re administration. AE is not related to concomitant medication or non-pharmacological factors (food, participant's own illness, environment, etc.);
- Probably related: The occurrence of AE is reasonably temporally related to the investigational drug. AE disappears or alleviates after discontinuation or reduction. AE is not related to concomitant medication or non-pharmacological factors;
- Possibly related: The occurrence of AE is reasonably temporally related to the investigational drug. Remission of the AE after discontinuation or reduction is unknown or insignificant, and other factors (e.g., participant's own illness, concomitant medication, or non-pharmacological factors) may also contribute to the event;

- Possibly unrelated: The time relationship between the occurrence of AE and investigational drug administration is unclear. AE does not resolve after discontinuation or remission is unknown, and concomitant medication or non-pharmacological factors can explain the AE;
- Definitely unrelated: The occurrence of AE is not reasonably temporally related to the investigational drug and/or evidence exists that the AE is definitely related to concomitant medication or non-pharmacological factors.

Because this study is a single administration and does not involve observation of adverse events through dose reduction/discontinuation/re-use, the investigator should make a comprehensive judgment of relevance based on the metabolic and pharmacodynamic characteristics of the investigational drug and the participant's clinical presentation, as well as the possible presence of non-pharmacological factors. When there is a change in consistency among test individuals, it is more likely to be related to the investigational drug.

In order to minimize risk to the medication-using population and to comply with regulatory requirements, sponsors will address the relevance of the incident in the following manner:

- "Possibly unrelated", "Definitely unrelated", i.e. "unrelated", are categorized as unrelated adverse events;
- "Positively Related", "Probably Related", or "Possibly Related" should be considered "Related" and categorized as related adverse events.

8.5.5 Serious Adverse Event Reporting

8.5.5.1 Serious Adverse Event Reporting

When an investigator is informed of a serious adverse event in a participant during a clinical study, he or she should promptly manage and treat the event, whether or not the serious adverse event is related to the investigational drug. It should also be reported immediately (within 24 hours) to the sponsor or the sponsor's designated representative, and the investigator should complete, sign and date the full Drug Serious Adverse Event Report Form.

For reports involving fatal events, the investigator should provide other required information such as autopsy reports and final medical reports to the sponsor and ethics committee.

